8.2.3.4 Last effectiveness for special population set

The last effectiveness analysis for special population set is included as factor analysis of last effectiveness in this SAP 8.2.3.3.

8.2.3.5 Effectiveness(Best overall response)

In order to identify effectiveness (best overall response) of BESPONSA®, the 'effectiveness' is judged as follows based on the best overall response during evaluation and summarized by the number of subjects(n), percentage(%) and 95% confidence interval of percentage.

- Effective: CR, CRI
- Ineffective: Refractory disease, Progressive disease, Relapsed disease

8.2.3.6 Factor analysis of effectiveness based on best overall response

To identify factors that may be associated with effectiveness based on best overall response, effectiveness according to the background factors in section 8.2.1 and special population set in section 5.3 shall be summarized using the number of subjects(n), percentage(%) and 95% confidence interval of percentage. In addition, to explore the factors that affect effectiveness, univariate analyses based on a Chi-square test or Fisher's exact test (when cells with an expected frequency of less than 5 exceed 20% of total cells) and logistic regression shall be used to assess the impact of each background factor on the effectiveness and p-value will be provided.

For the final re-examination report, potentially significant factors(p-value<0.05) identified by in the univariate analyses will be further explored and tested in a multiple logistic regression model. For final models, odds ratio, 95% confidence interval of odds ratio and p-value will be provided for each factor. If there is no potential significant factor identified in the univariate analyses, multivariate analysis with logistic regression will not be applied.

8.2.3.7 Effectiveness(Best overall response) for special population set

The effectiveness(best overall response) analysis for special population set is included as factor analysis of effectiveness in this SAP 8.2.3.6.

The following clauses from 8.2.3.8 to 8.2.3.10 are analysed to prepare a manuscript for publication.

8.2.3.5 Progression-free survival (PFS)

PFS is defined as time from date of enrollment to earliest date of the following events:

PFIZER CONFIDENTIAL

CT24-WI-GL03-RF02 3.0 *Non-Interventional Statistical Analysis Plan for Primary Data Collection Study*
Page 14 of 17

- Death
- Refractory disease
- Progressive disease
- Relapsed disease

Subjects without a PFS event at time of analysis will be censored at the last valid disease assessment. In addition, subjects with documentation of an event after an unacceptably long interval (>28 weeks if there was post-baseline disease assessment, or >12 weeks if there was no post-baseline assessment) since the previous disease assessment will be censored at the time of the previous assessment (date of enrollment if no post-baseline assessment). Post-study treatment follow-up disease assessments will be included.

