7.3.6. Administration status and response evaluation for each cycle of BESPONSA®

Record the following with regard to administrative status and response evaluation for each cycle. Record administrative status of all cycle until the last administration dose. Refer to LPD for posology and method of administration.

- Administration date

- Body surface area
- Administration dose
- Pre-medication: If 'conducted', record the detailed information in '4.Concomitant medication' clause in CRF.
- Response evaluation after each cycle: Record the evaluation date and response. Select one among 'CR', 'CRI', 'refractory disease', 'progressive disease', or 'relapsed disease'. Response Criteria is defined according to *NCCN Guideline Version 2.2016 Acute Lymphoblastic Leukemia*⁹. Refer to Appendix 1 for detailed Response Criteria. If response evaluation is not done, check 'undone' and leave the evaluation date blank.

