APPENDIX 1. RESPONSE CRITERIA

APPENDIX 1. RESPONSE CRITERIA

Response Criteria is defined according to 'NCCN Guideline Version 2.2016 Acute Lymphoblastic Leukemia⁹'.

The below outcome definitions will be used for reporting of response assessments.

Response Criteria for Blood and Bone Marrow:

- Complete response (CR)
 - No circulating blasts or extramedullary disease
 - No lymphadenopathy, splenomegaly, skin/gum infiltration/testicular mass/central nervous system involvement
 - Trilineage hematopoiesis and < 5% blasts
 - Absolute neutrophil count (ANC) > 1000/microL
 - Platelets > 100,000/microL
 - No recurrence for 4 weeks
- CR with incomplete blood count recovery (CRi)
 - Meets all criteria for CR except platelet count and/or ANC
- Refractory disease
 - Failure to achieve CR at the end of induction
- Progressive disease
 - Increase of at least 25% in the absolute number of circulating or bone marrow blasts or development of extramedullary disease
- Relapsed disease
 - Reappearance of blasts in the blood or bone marrow (>5%) or in any extramedullary site after a CR

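### PFS counts the earliest refractory entry even when CR/CRi follows, so a late responder can be a PFS failure, 'Effective' in best overall response, and have a duration of remission that ends before it starts

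*SAP*

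**What the plan says.** **PFS.** SAP 8.2.3.5 Progression-free survival: "PFS is defined as time from date of enrollment to earliest date of the following events". The four events are death, "Refractory disease", progressive disease and relapsed disease. The refractory item carries no qualifier: it is not tied to the final evaluation, to a particular cycle, or to patients who never respond.

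**What is recorded.** Protocol 7.3.6: "Response evaluation after each cycle: Record the evaluation date and response". The options are: "Select one among 'CR', 'CRI', 'refractory disease', 'progressive disease', or 'relapsed disease". The only other entry is for a missing evaluation: "If response evaluation is not done, check 'undone' and leave the evaluation date blank". SAP 6.2 and 8.2.3.1 carry the same five categories into the per-cycle analysis.

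**Definition of refractory.** Protocol Appendix 1: "Failure to achieve CR at the end of induction". Neither document says which BESPONSA cycle ends induction.

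**Best overall response.** SAP 8.2.3.5 Effectiveness (Best overall response; the section number is used twice) judges effectiveness "based on the best overall response during evaluation" and classes CR and CRi as effective.

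**DoR.** SAP 8.2.3.7 Duration of Remission runs from the first CR/CRi to the PFS event as defined above.

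**The concern.** Take a patient evaluated after cycle 1 who is not in CR/CRi, has not progressed and has no earlier CR on BESPONSA to relapse from. The only category left on the form is refractory disease. If the patient reaches CR/CRi at a later cycle, the earlier entry remains the earliest listed event. PFS then ends at an evaluation before the remission, while the response table counts the same patient as a success.

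What is at stake is the PFS table and curve planned for the manuscript (SAP section 9, Section II, Table 1 and Figure 1) and the DoR curve (Figure 3). A superseded refractory entry can only shorten PFS, so the direction of the bias is known. Repairing DoR alone would leave the PFS curve unchanged.

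**Working it through.** The documents give no PFS figure, late-response rate or evaluation calendar, so there is no stated figure to reproduce. The check applies the rules to one patient and then shows the scale under stated assumptions.

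**1. One patient.** Assumed dates, counted from enrollment: refractory at day 21 (after cycle 1), CR/CRi at day 42 (after cycle 2), relapse at day 222.

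| Quantity | SAP as written | Superseded entry not counted |
|---|---|---|
| PFS | 21 days, event | 222 days, event |
| Best overall response | Effective | Effective |
| DoR | 21 − 42 = −21 days | 222 − 42 = 180 days |

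**2. Does another rule remove the day-21 event?** The long-interval rule censors an event that comes too late after the previous assessment; for a first assessment the limit is ">12 weeks if there was no post-baseline assessment". A cycle-1 evaluation within 12 weeks of enrollment is not removed. SAP 8.2.1.5 tabulates one to six cycles, so a first response after cycle 1 is possible.

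**3. Share of patients misclassified.** Let r be the share who ever reach CR/CRi and late the share of these who first do so after cycle 1. Assume that all are evaluated after cycle 1 and that late responders are coded refractory then. The share is r × late:
- r = 0.7, late = 0.2: 0.7 × 0.2 = 0.14, or 14 of the planned 100 patients
- r = 0.7, late = 0.3: 0.7 × 0.3 = 0.21, or 21 of 100
- wider range: 0.5 × 0.1 = 0.05 to 0.7 × 0.5 = 0.35, or 5 to 35 of 100

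**4. Effect on the PFS curve (illustration).** Further assumptions: evaluations at day c and day 2c, late responders first respond at 2c, exponential remission with a median of 180 days, no censoring. Never-responders are placed at day c under both rules, so the difference comes from the late responders alone.

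- As written: S(90) = r(1 − late) × 2^(−(90 − c)/180)
- Superseded entry not counted: add r × late × 2^(−(90 − 2c)/180)

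For c = 21, r = 0.7, late = 0.2: 0.56 × 2^(−69/180) = 0.56 × 0.767 = 0.429. Adding 0.14 × 2^(−48/180) = 0.14 × 0.831 = 0.116 gives 0.546 (unrounded terms).

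| c | r | late | PFS at day 90, written / corrected | Median PFS (days), written / corrected |
|---|---|---|---|---|
| 21 | 0.5 | 0.1 | 0.345 / 0.387 | 21 / 21 |
| 21 | 0.7 | 0.2 | 0.429 / 0.546 | 50 / 113 |
| 28 | 0.7 | 0.2 | 0.441 / 0.564 | 57 / 121 |
| 21 | 0.7 | 0.3 | 0.376 / 0.550 | 21 / 115 |
| 28 | 0.7 | 0.5 | 0.276 / 0.583 | 28 / 130 |

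The medians are where each curve reaches 0.5. A simulation under the same assumptions agrees within sampling error.

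**The case against.** **Appendix 1 already limits the term.** Protocol 7.3.6 says responses follow Appendix 1, which ties refractory disease to the end of induction. On that reading, a patient still in induction after cycle 1 is not refractory and has no event. This is the strongest objection, and it shows that the literal reading is not the only one. It does not cure the problem. Induction is not mapped to any BESPONSA cycle, the form applies the category after each cycle, and barring an early refractory entry would leave this patient with no valid category. Stating which cycle ends induction would not be enough either, because a response after that cycle would produce the same conflict.

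**Not every slow responder is affected.** A reader might infer that each of them fails at the first evaluation. The documents do not support that. A cycle may be marked as not done, sites may follow Appendix 1, and nothing shows how often cycle 1 is evaluated in routine practice. This stands, and the shares above are upper values for given r and late.

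**The median need not collapse.** A reader might also infer that median PFS falls to the first evaluation date. With all patients evaluated and never-responders also failing at that evaluation, the share failing then is (1 − r) + r × late. This is 0.30 + 0.14 = 0.44 in one case, which leaves the median later, and 0.30 + 0.21 = 0.51 in the other, which does not. With r = 0.5 the median sits at the first evaluation under either rule.

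**Limited reach.** PFS, OS and DoR are for a manuscript (SAP 8.2.3.7, special population set, closing sentence), PFS is not a protocol effectiveness parameter (Protocol 7.7.2), and there is no formal hypothesis (SAP 4). All true. Nor is a difference between endpoints an error in itself: last effectiveness and best overall response may legitimately differ. A remission that ends before it begins is a different matter.

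**Conclusion.** The point holds. As written, the PFS rule counts a refractory entry that a later CR/CRi has superseded. It then conflicts with best overall response and gives DoR a negative length for the same patient. The bias in PFS is downward.

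Its size cannot be taken from the documents. With everyone evaluated after cycle 1, 14% (21%) of patients are misclassified for an assumed 70% response with 20% (30%) late; the assumed range examined is 5% to 35%. The curve and median figures also rest on assumed evaluation dates and remission length. The regulatory effectiveness tables and OS are unaffected. The rule should be corrected before the publication analyses are programmed.

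**What to change.** In SAP 8.2.3.5 Progression-free survival, add:
- A refractory entry is not a PFS event if CR/CRi is recorded at a later BESPONSA evaluation. A refractory entry with no later CR/CRi remains an event, including one recorded after an earlier CR/CRi.
- For patients who never reach CR/CRi, the date of the refractory event is fixed in advance. One option is the final effectiveness evaluation or, if missing, the last cycle evaluation, which is the fallback already used for last effectiveness (SAP 6.2 and 8.2.3.2). A sensitivity analysis uses the first refractory entry.
- Death, progressive disease and relapse keep their own dates.

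In SAP 8.2.3.7 Duration of Remission, count only PFS events after the first response.

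**Cost.** A few SAP sentences and one extra PFS run, on data already collected; treatment is not touched. The drawback is that under the main dating rule never-responders' event dates move later and partly follow treatment duration. The sensitivity analysis shows how much that matters.

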7.2.3. Duration of the study

According to MFDS re-examination regulation, the re-examination report based on collected data of 6 years must be submitted to MFDS within 3 months after the end of specified re-examination period (from the product approval date to 6 years afterwards).

The data collection period of this study is until the required subject number (100 patients) is collected. The observation period for each subject is from initiating administration of first dose of BESPONSA® to the end of the observation period of the study, which must include at least 28 calendar days following the last administration of a BESPONSA®. In case of patient that Hematopoietic Stem Cell Transplant (HSCT) after administrated BESPONSA®, follow-up until 180 days after transplantation. All the data collected during the observation period should be recorded in the case report form (CRF). In case of an adverse event/safety event recognized after the observation period ends, it should be recorded in the CRF as specified in Section 7.

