7.3.7. Final effectiveness evaluation

Record the final effectiveness after all cycle of BESPONSA® is finished.

Check 'conducted' if final effectiveness is evaluated then record the date of evaluation. Check 'not conducted' if final effectiveness is not evaluated then select one reason why it is not conducted among 'death', 'follow up loss', or 'other'. If 'other', record the specific reason.

- Response criteria: Select one among 'CR', 'CRI', 'refractory disease', 'progressive disease', or 'Relapsed disease'.
- Plan for HCT: Check 'yes' if HCT is on plan or on ongoing for a subject.

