7.7.2. Effectiveness analysis

- Effectiveness parameter
 - Response after each cycle: CR, CRi, Refractory disease, Progressive disease, Relapsed disease
 - Final effectiveness: CR, CRi, Refractory disease, Progressive disease, Relapsed disease

- Effectiveness parameters will be descriptively summarized. If necessary, χ^2 -test, paired t-test, analysis by repeated measurement, and other statistical methods will be used.

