8.2.3.7 Duration of Remission (DoR)

DoR is defined as time from date of first response in responders (CR/CRi by investigator assessment) to date of PFS event (see definition of PFS above). Responders without PFS event will be censored at the last valid disease assessment including follow-up disease assessment.

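### PFS and DoR rely on post-treatment disease assessments for which the protocol lists no response field, so deaths and non-fatal relapses after the final evaluation are captured unevenly

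*SAP*

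**What the plan says.** The SAP sections headed Progression-free survival and Duration of Remission define these endpoints for a manuscript. They are numbered 8.2.3.5 and 8.2.3.7, numbers also used for best-overall-response sections.

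- PFS events are death, refractory, progressive and relapsed disease. On censoring: "Subjects without a PFS event at time of analysis will be censored at the last valid disease assessment". On later data: "Post-study treatment follow-up disease assessments will be included".
- An event found too long after the previous assessment is censored back to that assessment. The limit is ">28 weeks if there was post-baseline disease assessment".
- DoR runs from first CR/CRi to a PFS event. Otherwise: "Responders without PFS event will be censored at the last valid disease assessment including follow-up disease assessment".

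The protocol's response data are:

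- Section 7.3.6: "Response evaluation after each cycle: Record the evaluation date and response". An evaluation may be marked as not done.
- Section 7.3.7: "Record the final effectiveness after all cycle of BESPONSA® is finished". No timing is set. The same form asks whether HCT is planned or ongoing.
- Section 7.7.2 names only two effectiveness parameters, response after each cycle and the final one: "Final effectiveness: CR, CRi, Refractory disease, Progressive disease, Relapsed disease". SAP 6.2 follows the same two points.

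Observation lasts longer than this. Protocol 7.2.3 sets a period "which must include at least 28 calendar days following the last administration of a BESPONSA", and follow-up to 180 days after HSCT. It ties no disease assessment to either window.

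**The concern.** The SAP's event and censoring rules presuppose repeated, dated disease assessments after treatment. The protocol describes follow-up time but lists no response item to fill it. Deaths and relapses in that time then enter PFS and DoR by different doors, and the SAP opens only one of them explicitly.

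Two distortions can follow, in opposite directions. Relapses are missed, or are dated at a later death, which lengthens apparent remission. Meanwhile event-free survivors leave the risk set at the final evaluation while patients who later die stay in it, which shortens apparent remission in a Kaplan-Meier type estimate. (The SAP names no estimator.) A published DoR or PFS would mix the two, and the reader could not tell how much of the curve reflects relapse.

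**Working it through.** The documents give no event count, median or censoring rate for PFS or DoR, so there is no planned figure to reproduce.

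**1. What can be recorded after the final evaluation**

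| Occurrence | Where the protocol records it | Does the SAP count it for PFS/DoR? |
|---|---|---|
| Death | SAE; fatal malignancy in the reporting period as Grade 5 (7.3.8.2) | Yes, subject to the long-gap rule |
| Non-fatal relapse or progression | AE with onset date (7.3.8.1, 7.3.8.3, 9.1); no response field listed | Not stated |
| Continued remission | No field listed | Would move the censoring date if it were recorded |

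Take two transplanted responders with the same final evaluation. Both relapse at the same time after HSCT. One dies before day 180 and, if the long-gap rule is met, is an event dated at death. The other is alive at day 180. On the listed response fields, that patient is censored as relapse-free at the final evaluation.

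**2. The long-gap rule**

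28 weeks × 7 = 196 days, and 196 − 180 = 16 days. With no later assessment, a death on day 180 after HSCT counts only if the last assessment was within 16 days before HSCT. Otherwise the patient is censored back to that assessment. A death within 28 days of the last dose will normally be inside the limit.

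**3. Illustration of size (assumed values)**

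Let m be the true median DoR and w the time from first response to final evaluation, both in months. With exponential times, the share of responders with no event by the final evaluation is exp(−ln 2 × w/m):

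| m | w = 1 | w = 3 | w = 5 |
|---|---|---|---|
| 3 | 79% | 50% | 31% |
| 6 | 89% | 71% | 56% |
| 12 | 94% | 84% | 75% |

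A simulation (400,000 responders per setting) then added deaths counted after the final evaluation. Its assumptions were:

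- m and w as in the table.
- A fraction p = 20% or 40% of first events are deaths without relapse. The relapse hazard is (1 − p) × ln 2/m and the death hazard is p × ln 2/m.
- Median survival after relapse is 4.5 months, the middle of the 3–6 months that Protocol section 5 gives for relapsed or refractory adults in general.
- Follow-up after the final evaluation is 28/30.44 = 0.92 months, or 180/30.44 + 0.5 = 6.41 months for HSCT. The extra half month (about 15 days) before HSCT keeps deaths inside the 16-day margin.

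| | 28-day follow-up | 180 days after HSCT |
|---|---|---|
| Example (m = 6, w = 3, p = 20%): event by final evaluation | 29% | 29% |
| Example: later death counted | 2% | 19% |
| Example: censored at final evaluation | 69% | 51% |
| Example: relapsed in follow-up, still alive, no response field | 5% | 18% |
| All settings: censored at final evaluation | 29–93% | 15–79% |
| All settings: relapsed in follow-up, still alive, no response field | 2–11% | 8–28% |

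The relapsed-and-alive group is part of the censored group. The 28-day column takes the final evaluation as falling at the last dose; a later evaluation shortens the gap.

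**The case against.** The strongest reply is that the protocol does collect disease information after treatment. Progression or worsening of the disease is listed as an example of an AE. Every AE in the observation period needs an onset date and goes on the CRF, and the restriction in 7.3.8.2 concerns SAE reporting only. Lack of efficacy is also recorded. The final evaluation is itself post-treatment, has no fixed timing and offers relapsed disease as a category, so the SAP sentence could refer to it. The full CRF is not in the documents, and the SAP uses items that Protocol 7.3 does not list, such as a check that AE status was evaluated (SAP 5.1) and a completion/discontinuation date (OS). An additional follow-up field cannot be ruled out.

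All of this stands, and it limits the point. A reader might infer that no relapse information exists after treatment; the AE route contradicts that. A reader might also infer that the medians will be inestimable or driven by deaths alone. For PFS this is wrong, because refractory, progressive and relapsed disease at cycle and final evaluations are events. DoR likewise captures relapse up to the final evaluation.

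The reply does not supply the missing rule. Neither SAP section says that an AE record of progression is a disease assessment or an event, and a general duty to record collected data creates no field, schedule or definition.

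**Conclusion.** The mismatch holds. The SAP counts and censors on follow-up disease assessments, while the protocol lists no response or relapse field after the single final evaluation. After that evaluation deaths can count, but whether a non-fatal relapse counts is left unsaid. Censoring may therefore be informative, and the net direction of bias cannot be determined from the documents.

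The size is unknown. The percentages above rest on assumed DoR, evaluation timing and share of deaths without relapse, and on no extra CRF field and no use of AE records. It is tempting to say that remission duration is mostly cut off at the final evaluation. The illustration exceeds half in many settings but falls to 29% with 28-day follow-up and 15% with HSCT follow-up, so the documents do not support that. Nor do they support a fixed loss of at least 28 days per patient, since the final evaluation has no set date.

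PFS and DoR are publication-only analyses in a study without a formal hypothesis. The MFDS re-examination tables are unaffected. The point should be settled before the manuscript analysis is run.

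**What to change.** Change the SAP wording in one of two ways.

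- **(a) Use the AE records.** State that AE-recorded progression or relapse is a PFS/DoR event, dated at AE onset, and report how many event-free responders are censored at the final evaluation. Cost: event dating is less standardised than by response criteria. Event-free survivors are still censored earlier than deaths and relapses are counted, which is why that number must be shown.
- **(b) Cut off at the final evaluation.** Delete the follow-up wording from both sections, apply the same cut-off to deaths and relapses, and label the endpoints as PFS and DoR through the final evaluation. Cost: a narrower claim in the manuscript.

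If a protocol and CRF amendment is still feasible, it would be better to abstract from the chart disease status with date at last contact, and the date of first post-treatment relapse. That costs an amendment, IRB/IEC approval where applicable and a return to the charts, against a planned end of data collection of 2 Jan 2025. If such a field already exists, the SAP need only name it and define which follow-up assessments are valid.
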